#### **Treatment Overview.**

**Randomization.** All eligible participants who provide written informed consent and complete the baseline survey will be stratified by race and gender and randomized 1:1 to either menthol or Virginia tobacco EC. Randomization will be determined by computer-generated random numbers. Randomization assignments will be placed in sealed envelopes with sequential study ID numbers. After baseline data collection has been completed, the research assistant will select the sequential study ID number to determine the randomization assignment.

**EC (Weeks 0-12).** Participants will be provided a 12-week supply of VUSE 5% nicotine concentration in either menthol or Virginia tobacco that will be dispensed at the weeks 0, 4, and 8 in-person visits (4-week supply @ each visit). One pod delivers the equivalent of one pack of cigarettes, with variability of 13-30 cigarettes based on user,  and therefore allocation will be based on 1 pod per pack of cigarettes at week 0 and on current use patterns at weeks 4 and 8.

**EC use.** Participants will be instructed to use only the study EC in the flavor provided but to report all ECs by timeline follow-back at follow-up visits. To aid in recall and assessment of fidelity to protocol, participants will be given dated bags to collect all EC. Bags will be returned at each visit during the intervention phase to confirm use of EC (i.e., grams of e-liquid consumed and count of pods) as well as protocol adherence (i.e., the number of pods/grams vaped in the study provided versus non-study provided flavor) (see Measures). Those not attending EC dispensing visits will be reached by phone and delivered enough to get them to the next dispensing time point. Participants will be compensated for returned pods, but earnings will not be tied to protocol adherence. Participants will be paid for returned pods even if they return non-study provided EC to increase honest reporting.

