#### **B. Outcome**

#### EFFECTIVENESS (Aims 1 & 4).

Switching (Primary Outcome). The primary outcome is the proportion of menthol smokers who make a complete or predominant switch to EC, defined as use of EC along with a > 50% reduction in cigarettes from baseline to week 12. The 7-day Timeline Follow Back Interview (TLFB) will be used to assess participants cigarette and EC use patterns each day for the past 7 days at each visit (weeks 0, 4, 8, 12, 18, 26). The primary endpoint is, however, fixed at week 12. The TLFB is a reliable and valid way of collecting information about substance use quantity and frequency and, in tobacco research, has been corroborated against interactive voice response, butt counts (storing and returning the butts of cigarettes smoked), and biological measures for cigarettes smoked and puff topography for EC, supporting the strong validity of this self-report measure compared to other 'gold standard' measures. For each of the last 7 days participants will be asked to recall the number of cigarettes smoked and EC sessions vaped; following standard practice, an EC session is defined as at least 15 puffs or lasting around 10 minutes. For each EC session, participants will be asked to specify the device used (i.e., study provided versus something else) and the flavor (i.e., menthol, Virginia tobacco, something else).\* For non-study provided EC, detailed information will be collected about the type of EC (e.g., brand, podbased, disposable, refillable), flavor, nicotine concentration and, if available, whether the product is nicotine salt-based. To aid in recall and corroborate self-report, participants will be given dated bags to collect all EC. Bags will be returned at each visit during the intervention phase and used to confirm use of study provided EC (i.e., grams of e-liquid consumed) and protocol adherence (i.e., the number of pods vaped in the study provided versus non-study provided flavor). *Complete switching* is defined as any use of EC and no use of cigarettes in the past 7 days (i.e., 100% reduction in CPD from baseline), biochemically confirmed with an expired breath CO < 6 parts per million (ppm). CO is used for verification because cigarettes produce carbon monoxide as a byproduct of combustion, while heating an e-liquid does not generate CO. The < 6 ppm CO cutoff is more conservative than the  $\leq$  10 ppm cutoff that is commonly used and reflects the current state of knowledge for detecting recent cigarette smoking. Predominant switching is defined as those who report any use of EC along with a > 50%reduction from baseline in CPD. A > 50% reduction has been selected because it is a measure of acceptability of the EC products and is associated with substantial reductions in biomarkers of harm and exposure relative to continued smoking and is a common endpoint used in tobacco harm reduction studies. Partial switching will be defined as those who report any use of EC along with a  $\leq$  50% reduction from baseline in CPD. No switching (i.e., exclusive cigarette user) will be defined as those who reported no use of ECs and any use of cigarettes in the past 7 days. A potential fourth group, no use of e-cigarettes or combustible cigarettes, may occur. For all switching trajectories, use of EC will be corroborated with pod counts and objectively measured EC pod weights during the intervention phase.

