#### Biomarkers of interest include:

cotinine

- total NNAL (for nicotine-derived nitrosamine ketone NNK);
- 2-hydroxyethylmercapturic acid (HEMA) (for ethylene oxide);
- 2-hydroxy-3-butenyl-mercapturic acid and isomers (MHBMA) (for 1,3-butadiene);
- 3-hydroxy-1-methyl propyl-mercapturic acid (HMPMA) (for crotonaldehyde);
- 3-hydroxypropylmercapturic acid (3-HPMA) (for acrolein);

- S-phenylmercapturic acid (S-PMA) (for benzene);
- 2-cyanoethylmercapturic acid (CEMA) (for acrylonitrile);
- 2-hydroxypropylmercapturic acid (2-HPMA) (for propylene oxide)
- pyrene (1-OHP)
- matrix metalloproteinaise-8 (MMP8) and interleukin-9 (IL9) for airway epithelial cell inflammation
- 8-Epi-prostaglandin F2a (oxidative stress)
- 11-Dehydrothromboxane B2 (platelet activation)
- soluble intercellular adhesion molecule-1 (sICAM)

**ACCEPTABILITY (Aim 3).** Detailed assessment of EC product use, effects on withdrawal, craving, and dependence, and subjective and sensorial effects will be evaluated at all study visits to compare acceptability by group (menthol versus tobacco EC).

**Grams of study e-liquid consumed (weeks 4, 8, 12).** Use of the study EC in the flavor provided will be objectively measured by asking participants to bring all used, unused, or partially used pods to the weeks 4, 8, and 12 study visits. Pods will be weighed prior to their distribution and then upon return to derive *total grams of study e-liquid in the flavor provided consumed* from weeks 0-12. In our RCT, 95%, 92%, and 98% of participants returned their pods at weeks 2, 4, and 6, respectively, and there was no evidence of cheating – i.e., returned pods were in the flavor provided by the study – suggesting that participants used only the study provided pods throughout the intervention phase. For unreturned pods, we will conservatively assume 0 grams of e-liquid consumed. Objective measurement of pod weights was strongly correlated with number of e-cigarette sessions per day measured by TLFB in our RCT (r=0.58, p < .001).

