**Flavor usage (all visits).** Based on our RCT, we expect low rates of non-study EC product use, but we will conduct rigorous assessments of adherence to EC flavoring during the intervention phase and continued use during the long-term follow-up phase. From the TLFB, we will summarize the proportion of total EC that were in the study provided versus a non-study provided flavor. From pod counts, we will summarize the number of pods returned by flavor (i.e., menthol, Virginia tobacco, other) and derive an estimate of the proportion of total pods returned that were in the study provided flavor.

**Craving (all visits).** Craving for cigarettes will be assessed using the *Questionnaire on Smoking Urges-Brief* **(QSU)** and its companion, the *Questionnaire on Vaping Craving-Brief* (*QVC*) will be assessed at each visit and compared between groups. Both measures yield a total score and two factor scores: desire to smoke/vape and intention to smoke/vape. The QVC yields a third factor, positive outcome of vaping.

**Withdrawal (all visits)**. The *Minnesota Tobacco Withdrawal Scale*will be used to rate eight withdrawal symptoms in the past 24 hours: anger, anxiety, concentration, craving, hunger, sadness, and sleep. Items are rated from 1 (strongly disagree) to 5 (strongly agree). Scores will be summarized overall and for each construct.

**Dependence (all visits)**. Following guidance from the TCORS dependence workgroup, we will include a compendium of dependence measures, validated for use in assessing both cigarette and EC related dependence, to cover all components of dependence (i.e., quantity and frequency of use, tolerance, perceived benefits, withdrawal symptoms, cravings/urges to use, use despite harm, impaired control, automaticity, preferred over competing rewards, and sensory dependence.) We have intentionally selected cigarette dependence measures that have parallel EC dependence measures to allow for direct comparison in dependence across products by group. These measures include:

• Patient Reported Outcomes Measurement Information System (PROMIS) Nicotine Dependence Item Bank  and its companion the *E-Cigarette Dependence Scale*.

• *Penn State Cigarette Dependence Index* (PS CDI) and its companion the *Penn State Electronic Cigarette Dependence Index* PS ECDI)

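### The pod-count flavour-adherence proportion credits unused study pods as adherence, so it dilutes flavour cross-over whenever off-flavour pods are also returned

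*Combined protocol and SAP*

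**What the plan says.** The *Flavor usage (all visits)* paragraph in section V.B gives the purpose: "we will conduct rigorous assessments of adherence to EC flavoring during the intervention phase". It names two sources.

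- From the timeline follow-back (TLFB): "we will summarize the proportion of total EC that were in the study provided versus a non-study provided flavor".
- From pod counts: returned pods are tabulated as menthol, Virginia tobacco or other, and the investigators will then "derive an estimate of the proportion of total pods returned that were in the study provided flavor". Nothing limits this to pods that were used.

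The preceding paragraph, *Grams of study e-liquid consumed*, says what comes back. Use is measured by "asking participants to bring all used, unused, or partially used pods to the weeks 4, 8, and 12 study visits". It adds: "Pods will be weighed prior to their distribution and then upon return". An unopened study pod can therefore be told from a vaped one.

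Two other places describe protocol adherence by use. The *EC use* paragraph under Treatment Overview (II.E) has "the number of pods/grams vaped in the study provided versus non-study provided flavor". The *Switching (Primary Outcome)* paragraph (V.B) has "the number of pods vaped in the study provided versus non-study provided flavor".

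Treatment Overview also sets the supply: one pod per pack smoked at week 0, then current use at weeks 4 and 8. Dated bags collect all e-cigarette products, and returned pods are paid for whatever their flavour.

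**The concern.** The Flavor usage paragraph is the only place that gives the pod-count proportion a numerator and a denominator, and it counts pods returned where the other two places speak of pods vaped. The two differ as soon as unused pods come back. Every dispensed pod is in the assigned flavour, so an unopened one enters both numerator and denominator as if it showed adherence. The overstatement is largest for the participant who uses the assigned flavour least.

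Both ingredients are foreseeable. Week-0 supply follows smoking level, not vaping, so people who switch only partly, or who dislike the flavour, will have pods left over. Payment regardless of flavour invites off-flavour pods into the bags.

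What is at stake is interpretation. The trial is an open-label non-inferiority comparison of flavours, and switching counts any e-cigarette use whatever its flavour. Tobacco-arm participants who move to menthol products would tend to make the arms alike. Readers will look to the adherence data to judge how far that happened.

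**Working it through.** The plan states no figure for this measure, so there is none to reproduce. The check is algebra with assumed inputs.

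**Notation.** D = study pods dispensed; u = study pods vaped; n = off-flavour pods vaped and returned; r = fraction of unused study pods returned. For simplicity, all non-study pods here are off-flavour and all are returned.

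**Formulas**

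- Rule as written, r = 1: D/(D + n)
- Share of vaped pods: u/(u + n)
- Difference: n(D − u) / [(D + n)(u + n)]
- General r: [u + r(D − u)] / [u + r(D − u) + n]

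The difference is positive exactly when n > 0 and u < D, that is, when off-flavour and unused study pods both come back. If either is absent, this bias is zero.

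**Reported proportion by true share of vaped pods in the assigned flavour**

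| True share | r = 1, total vaped = D | r = 1, total vaped = D/2 | r = 0.5, total vaped = D |
|---|---|---|---|
| 75% | 80% | 89% | 78% |
| 50% | 67% | 80% | 60% |
| 25% | 57% | 73% | 45% |
| 0% | 50% | 67% | 33% |

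For example, with a true share of 50% and total vaped equal to D, u = n = 0.5D, so the rule gives D/1.5D = 67%. With no study pods vaped and n = D, it gives D/2D = 50%.

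**One illustrative participant.** At 10 cigarettes a day, and assuming 20 to a pack, the week-0 rule gives 10 × 28 / 20 = 14 pods. The values of u and n below are assumed.

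- 13 study pods vaped, 1 off-flavour: rule 14/15 = 93%; vaped 13/14 = 93%.
- 4 study pods vaped, 6 off-flavour: rule 14/20 = 70%; vaped 4/10 = 40%.

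Now carry both to 12 weeks, repeating the same use each period and assuming that weeks 4 and 8 are supplied to match study pods used.

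- First: D = 14 + 13 + 13 = 40, u = 39, n = 3. Rule 40/43 = 93%; vaped 39/42 = 93%.
- Second: D = 14 + 4 + 4 = 22, u = 12, n = 18. Rule 22/40 = 55%; vaped 12/30 = 40%.

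Matching supply to use shrinks the bias but does not remove it.

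**After correction.** Limiting both terms to used pods gives u/(u + n), the true share, provided all used off-flavour pods come back. Under-return of those pods is a separate problem that this change does not cure: with no unused pods returned and only half the off-flavour pods returned, a true 50% reads 0.5/(0.5 + 0.25) = 67%.

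**The case against.** The best defence is that the intent is already right: two places define adherence by use, the study-pod weights are collected, and a sensible analyst would apply them. The plan also expects little non-study use, and when n is small the bias is small, as the first illustrative participant shows. That argues for a light correction. It does not make the stated rule correct, because an analyst following the Flavor usage paragraph literally would include unused pods.

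Four stronger readings are tempting, and the documents do not support them.

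- *That the rule hides cross-over.* It dilutes it. Any returned off-flavour pod takes the figure below 100%, and the counts by flavour still show those pods.
- *That this is the only physical check.* Study-pod grams are another, and Aim 3 compares them between arms. In the second illustration they would show roughly 4/14 = 29% of the first supply used. The check is partial: grams cover study e-liquid only, and low grams may mean little vaping rather than cross-over. The TLFB share also lacks this flaw and captures non-pod devices, but it is self-reported and covers 7 days at each of weeks 4, 8 and 12, or 21 of 84 days.
- *That the plan's conclusion from its earlier trial fails for the same reason.* There the returned pods were all in the study flavour. With n = 0 and u > 0 both formulas give 100%, so unused pods do no harm. Whether off-flavour pods were withheld is another question.
- *That a large difference in adherence between arms would be cut by more than half.* If one arm resembled the first illustration and the other the second, the true gap of 93 − 40 = 53 points would read 93 − 70 = 23 over four weeks, but 93 − 55 = 38 over twelve. All of these rest on assumed pod counts.

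**Conclusion.** Wrong as written; minor. The direction is certain: when unused study pods and off-flavour pods are both returned, the stated proportion exceeds the share of vaped pods in the assigned flavour. The size is unknown, because the documents give no numbers of unused or off-flavour pods. Under the assumptions in the table, a true 50% reads as 60% to 80%, and complete cross-over reads as 33% to 67%.

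The proportion is a secondary description with no test or threshold attached, and no stated analysis population depends on it. The primary confidence interval, the handling of missing outcomes and the sample size are unaffected.

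**What to change.** Reconcile the Flavor usage paragraph with the EC use and Switching paragraphs by defining the proportion on used pods only.

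- Numerator: used pods in the assigned flavour. A study pod is used when its return weight is below its pre-dispensing weight by more than a stated tolerance.
- Denominator: all used pods of any flavour.
- Classify non-study pods by their flavour, not by being non-study. Otherwise a menthol-arm participant who buys menthol pods would be scored as a flavour cross-over.
- Report non-study product use, non-pod devices (disposables, refillables) and unused study pods on separate lines.

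The cost is a few sentences and a filter on weights already collected for study pods. Staff must mark returned non-study pods as used or unused and record their flavour. The reported adherence figure may be less favourable.

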#### **OTHER CONSTRUCTS OF INTEREST**

#### Safety and tolerability

• *Side Effects.* A symptoms checklist will be used to assess participants experience (yes/no) of common smoking/vaping related side effects, including cough, dry mouth, shortness of breath, mouth and throat irritation, headache, dizziness, nausea or vomiting, and increased heart rate/palpitations. For each side effect reported, participants will be asked whether they attribute the side effect to cigarettes, EC, or both.

• *Safety.* Adverse events observed or reported will be recorded at each in-person visit. Assessments as to seriousness, severity, and the relationship to treatment and other causes will be made. Serious adverse events will also be captured in the centralized database. AEs and SAEs will be reported to the appropriate regulatory agencies.

#### **Descriptive measures** (Week 0)

• *Demographic variables* include gender, age, marital/cohabitation status, socioeconomic status, psychiatric history, depressive symptoms (PHQ-9), and symptoms of generalized anxiety (GAD-7).

• *Psychosocial variables* include individual- (federal poverty level, financial strain, home ownership, housing stability) and area-level socioeconomic disadvantage (neighborhood social cohesion and trust, safety, and incivilities), race consciousness, experiences of discrimination, perceived stress, resilience, and history of trauma (i.e., adverse childhood experiences). These factors influence differences in smoking outcomes in racial/ethnic minority and socioeconomically disadvantaged smokers and were chosen for that reason.

• *Cigarette use history* will include cigarettes per day, age when started smoking regularly, length of time as a smoker, number of 24 hour quit attempts in the last year, length of the longest quit attempt, other smokers/vapers in the home, smoking/vaping status of partner and five best friends/family members.

#### C. Study results to participants

Study results will not be shared with participants.

#### **D.** Publication Plan

We plan to publish results in appropriate tobacco journals – e.g., JAMA, JNCI, Journal of General Internal Medicine, Addiction, Annals of Behavioral Medicine, Nicotine & Tobacco Research, Cancer Epidemiology, Biomarkers, & Prevention.

